### Other variables

Name	Method and metric	Time points
Age	
 
• Obtained from clinical records
 
• Mean (years)
 
	D0
Gender	
 
• Obtained from clinical records
 
• Proportion (male/female)
 
	D0
Body mass index	
 
• Obtained from clinical records
 
• Mean (kg/m^2)
 
	D0
PU risk	
 
• Scoring based on Charité standard
 
• Risk category (none/at risk/at high risk/at very high risk)
 
	D0 and once daily
PU risk	
 
• Scoring based on Braden score
 
• Mean (A.U.)
 
	D0 and once daily
Main and other medical diagnoses at admission	
 
• Obtained from clinical records
 
• Coding according ICD-10
 
	D0
Main and other medical diagnoses or procedures before the ICU stay (peripheral wards)	
 
• Obtained from clinical records
 
• Coding according ICD-10
 
• Coding according OPS version 2015
 
	D0
Diabetes mellitus	
 
• Obtained from clinical records
 
• yes/no
 
	D0
Tetraplegia	
 
• Obtained from clinical records
 
• yes/no
 
	D0
Length of stay on peripheral wards / type of ward before ICU transfer	
 
• Obtained from clinical records
 
• Mean (days)
 
	D0
Length of stay in emergency department	
 
• Obtained from clinical records
 
• Mean (hours)
 
	D0

[figure not shown]

Length of stay in operating room	
 
• Obtained from clinical records
 
• Mean (hours)
 
	D0, or if necessary
Length of stay in ICU	
 
• Obtained from clinical records
 
• Mean (days)
 
	D0 and once daily
Length of mechanical ventilation	
 
• Obtained from clinical records
 
• Mean (hours, days)
 
	D0 and once daily
Mean arterial blood pressure	
 
• Obtained from clinical records/monitoring
 
• Mean (mmHg)/24h
 
	D0 and once daily
Body temperature	
 
• Obtained from clinical records/monitoring
 
• Mean (°C)/24h
 
	D0 and once daily
Heart rate	
 
• Obtained from clinical records/monitoring
 
• Mean (beats/minute)
 
	D0 and once daily
Urine incontinence	
 
• Obtained from clinical records and direct observation
 
• Urine in direct contact with skin
 
• Mean (days)
 
	D0 and once daily
Stool incontinence	
 
• Obtained from clinical records and direct observation
 
• Stool in direct contact with skin
 
• Mean (days)
 
	D0 and once daily
Catecholamines	
 
• Obtained from clinical records
 
• Type (adrenalin, noradrenalin ...)
 
• Mean lengths of application (days)
 
• Mean doses (µl/kg/min)
 
	D0 and once daily
Support surface	
 
• Obtained from clinical records and direct observation
 
• Type (standard, special elastic foam, viscoelastic foam, low air loss overlay/mattress, alternating air mattress)
 
• Mean lengths stay on the support surface (days)
 
	D0 and once daily
Positioning	
 
• Obtained from clinical records and direct observation
 
• Type (30° degrees left/right, supine, prone, other)
 
• Mean lengths of position (hours)
 
	D0 and once daily
Smoker	
 
• Obtained from clinical records
 
• Proportion (yes/no)
 
	D0

### 3.5 Participant timeline

The expected flow of participants is shown in Figure 2. The time line of an individual patient is shown in Table 1.

Figure 2. Expected study flow chart

**Table 1. Patient timeline**

	Admission to ED and/or ICU	Follow-up	...	End of study
Days	D0	D1	D1 + 1	D1 + x
In-/exclusion criteria	X	X		
Informed consent	X*	X*	X*	X*
Demographics	X			
Skin inspection	X	X	X	X
Randomization	X			
Application of dressings	X			
Control of dressing fit/renewal	←—————→			
All other clinical variables	X	X	X	X
Ressource use (number of dressings, wound care materials)	X	X	X	X
Adverse events monitoring and documentation	←—————→			

\*Informed consent will be sought as soon as possible after inclusion.

### 3.6 Sample size

We are planning a study of independent cases and controls with 1 control per case. Prior data of the internal quality management indicate that the average PU incidence at the ICUs of the Charité is 0.06 per month. We expect that the cumulative PU incidence for experimental subjects will be 0.01 (RR 0.17). In order to test this hypothesis we will need to study 211 experimental patients and 211 control patients to be able to reject the null hypothesis that the PU incidence in the intervention and control groups is equal with a probability (power) of 0.8. The Type I error probability associated with this test of this null hypothesis is 0.05 (two-sided). We will use the chi-squared test statistic to evaluate this null hypothesis. To prevent a possible loss of follow-up of 10%, 464 patients in total are to be included. This total sample size is comparable to a previous trial using a similar intervention and design (Santamaria et al. 2013a). The “true” PU heel and sacral PU incidence in the study might be higher, because we will include only “high” and “very high risk” patients.

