#### 3.2 Eligibility criteria

##### Inclusion criteria

- Age 18+ years
- Major trauma and/or critically ill surgical and/or internal patients (e.g. with cardiac arrest) admitted to the emergency department and being transferred and/or admitted or directly to a surgical or internal ICU
- Major trauma and/or critically ill surgical and/or internal patients admitted through an in-house hospital transfer to a surgical or internal ICU (e.g. postoperative complications or acute deterioration of general health)
- Being at “high” or “very high” PU risk according to the Charité PU prevention standard:
  - Category 3 (=care dependent/limited bed mobility)
  - 4A (= high care depended, limited mobility in bed)
  - 4B (= high care dependent, totally immobile) according to the Jones classification modified by Charité
- Expected minimum length of stay at least three days
- Informed consent (or by legal representative)

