### 3.3 Interventions

Within the study PU prevention for all patients follows the Charité university hospital pressure ulcer prevention standard (Charité-Universitätsmedizin Berlin 2012) (Figure 1).

Figure 1. Current pressure ulcer prevention standard at the Charité

This includes PU risk scoring and skin inspection within 6 hours after admission and depending on the risk categories “high risk” and “very high risk” the implementation of preventive measures including: (1) patient information, (2) daily skin inspection, (3) mobilization, (4) use of special support surfaces, (5) repositioning and (6) floating heels. Regarding general skin and incontinence care there are no other standards implemented at the moment.

In case of potentially meeting the inclusion criteria for the study a researcher/research assistant of the CRC team will check the in- and exclusion criteria using a screening form. If eligible the assignment to one of the study groups will be performed by this researcher. This will be also done within 6 hours after admission **to the ICU**.

If a patient is assigned to the intervention group the dressings Mepilex® Border Sacrum and Mepilex® Border Heel will be applied by the researcher/research assistant onto the respective intact skin areas according to the instructions of the manufacturer and according to the study SOP (see Appendices 1 and 2). Special care will be taken that the Mepilex® Border Sacrum is carefully applied and that no other skin care products are used between the skin and the dressings. The dressings will be renewed every 3 days by the researcher/research assistant. In case of becoming soiled or dislodged they are changed immediately by the nurses and/or by the researchers. Nurses on the participating ICUs and on general wards will be instructed accordingly. In addition, in the intervention group laminated patient cards will be posted at and/or near the bed serving as reminder and containing minimum information about how to apply the dressings and the contact of the responsible researcher (Appendix 3). Dressings remain onto the skin during the whole study period also including transfer to another ward. All other PU preventive care and treatment procedures are performed as usual according to the Charité PU prevention standard (Figure 1).

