Skin and tissue inspections are conducted and study variables are collected daily by instructed researchers/research assistants/study nurses in agreement with the ICU and general ward staff. The following educational activities will be conducted before and during the trial:

- Initiation visit/kick-off meeting explaining the study design, procedures, data collection and documentation methods
- One hour skin and PU classification instruction, followed by an online examination PUCLAS3 (Beeckman, Schoonhoven 2014) for all study nurses/research assistants doing skin examinations
- Unannounced patient visits by the principle investigator for duplicate data collection and skin examination

Research assistants/study nurses/researchers follow up all included patients once daily for ensuring study compliance, monitoring correct dressing use and fit, doing skin inspections at the heels and sacral area and for monitoring the health condition including daily

documentation of PU risk and resource use regarding dressings and possible PU treatment (dressings, wound care procedures).

The study/follow-up ends if:

- The patient is no longer at “high” or “very high” PU risk according to the Charité standard (Figure 1) and if no sacral or heel PU developed or
- Complete healing of a within the study period developed heel or sacral PU or
- An adverse event (AE) related to the preventive dressings occurred or
- The patient wishes to withdraw or
- A severe form of protocol violation occurred (e.g. non-wearing of the dressings for more than 24 hours) or
- The patient dies or
- The patient is transferred to another care setting outside the Charité Campus Virchow or is discharged from the hospital

Adherence to the study protocol is improved using the following strategies:

- Kick-off meetings and training on the participating ICUs and EDs
- Subject cards at the bedside (Appendix 3)
- Once daily follow-up visits and assessments by researchers including checks of dressing fit
- Monthly status reports about recruitment on the participating wards
- Unannounced patient visits by the PI for duplicate data collection and skin examination

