### 3.4 Outcomes

#### Primary outcome

Name	Method and metric	Time points of data collection
Pressure ulcer category II, III, IV, Unstageable, DTI at heels or sacrum	
 
• Clinical assessment using the NPUAP/EPUAP 2014 PU classification system
 
• Proportions developed from baseline until end of study (cumulative incidence)
 
	D0 and once daily

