## Secondary outcomes

Name	Method and metric	Time points of data collection
Pressure ulcer category II, III, IV, Unstageable, DTI at heels or sacrum	
 
• Clinical assessment using the NPUAP PU classification system
 
• Proportions developed per 1000 bed days (incidence)
 
	D0 and once daily
Pressure ulcer category I (non-blanchable erythema) at heels and/or sacral area	
 
• Clinical assessment using the NPUAP PU classification system
 
• Proportions developed from baseline until end of study (cumulative incidence)
 
	D0 and once daily
Pressure ulcer category I (non-blanchable erythema) at heels and/or sacral area	
 
• Clinical assessment using the NPUAP PU classification system
 
• Proportions developed per 1000 bed days (incidence)
 
	D0 and once daily
Days free of sacral and/or heels pressure ulcers category I, II, III, IV, DTI	
 
• Clinical assessment using the NPUAP PU classification system
 
• Number
 
	D0 and once daily
Resources associated with heel and sacral PU prevention	
 
• Preventive dressings (n), time for dressing application (minutes; data source: estimation)
 
• Type of support surface (standard, special elastic foam, viscoelastic foam, low air loss overlay/mattress, alternating air mattress; data source: clinical records and direct observation)
 
• Type of turning (30° degrees left/right, supine, prone, other; data source: clinical records)
 
	D0 and once daily
Resources associated with heel and sacral PU treatment	
 
• Wound assessments (number and times; data source: clinical records and estimation)
 
• Wound infection diagnoses, e.g. swabs, biopsies (number, times; data source: clinical records and estimation)
 
• Therapeutic primary and secondary dressings (numbers, types), time for dressing application/changes (minutes; data source: clinical records and estimation)
 
• Debridement (numbers and types incl. material; data source: clinical records and estimation)
 
• Systemic antimicrobial treatment because of PU wound (number, types; data source: clinical records)
 
	D0 and once daily

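### Does the undefined ICU incidence of 0.06 per month undermine the sample size of 211 per arm?

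*Combined protocol and SAP*

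**What the plan says.** Section 3.6 gives one source for the control rate, the hospital's quality-management data, and reports that "the average PU incidence at the ICUs of the Charité is 0.06 per month". The next sentence sets the intervention-arm rate beside it: "We expect that the cumulative PU incidence for experimental subjects will be 0.01 (RR 0.17"). The ratio 0.01/0.06 is 0.17, so the first figure serves as the control arm's cumulative incidence. With 80% power, two-sided 5% alpha and a chi-squared test, the section arrives at 211 patients per arm, raised to 464 in total for a 10% loss. It adds a caveat that the true "PU heel and sacral PU incidence in the study might be higher, because we will include only" patients in the two upper risk classes.

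The primary outcome in section 3.4 is narrower than an ICU-wide ulcer rate. It counts category II, III, IV, unstageable or deep tissue injury at heels or sacrum, with the metric "Proportions developed from baseline until end of study (cumulative incidence"). The secondary outcomes use a separate metric with a time base, "Proportions developed per 1000 bed days (incidence").

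Follow-up has no fixed length. Section 3.3 lists several events that end it, among them: "The patient is transferred to another care setting outside the Charité Campus Virchow or is discharged from the hospital". It can continue after the ICU: "Dressings remain onto the skin during the whole study period also including transfer to another ward". The only stay length in the readable text is the inclusion criterion "Expected minimum length of stay at least three days"; Figure 2 is not readable in the copy reviewed.

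**The concern.** Two differently labelled quantities are compared as if they were the same. One is a monthly, ICU-wide figure with no stated denominator, site or category. The other is a per-patient proportion for two body sites and the more severe categories, over a stay whose expected length is not given. The protocol separates these two kinds of metric in its own outcome tables, so a reader is bound to ask which one 0.06 is.

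What is at stake is the stated 80% power. If the per-patient control risk of the primary outcome were well below 6%, because stays are shorter than a month or because the source figure includes other sites or category I, the trial would be less powerful than stated. If selecting high-risk patients pushes the risk above 6%, it would be more powerful. The caveat in section 3.6 names only the upward direction, and neither direction is entered in the calculation.

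**Working it through.** **Inputs (section 3.6).** Control 0.06, intervention 0.01, two-sided alpha 0.05, power 0.80, allocation 1:1, chi-squared test.

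**Reproducing the plan's figure.** Treat both rates as per-patient proportions, with mean (0.06 + 0.01)/2 = 0.035:

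n = [1.96·√(2·0.035·0.965) + 0.8416·√(0.06·0.94 + 0.01·0.99)]² / 0.05²
= (0.5094 + 0.2167)² / 0.0025 = 210.9, so 211 per arm.

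The arithmetic is right, and it shows how the authors used 0.06: as a cumulative proportion.

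**Sensitivity to the control risk.** The same formula solved for power at m per arm, control risk p and intervention risk q, with p̄ = (p + q)/2, is

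power = Φ{[(p − q)·√m − 1.96·√(2p̄(1 − p̄))] / √(p(1 − p) + q(1 − q))}.

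Example with p = 0.04, q = p/6 = 0.00667, m = 211: the numerator is 0.0333·14.526 − 1.96·0.2135 = 0.0658, the denominator is 0.2122, and Φ(0.310) = 0.622.

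With the relative risk held at 1/6 (an assumption outside the 6% row) and 211 per arm:

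| Control risk | Power, plan's formula | Power, exact, uncorrected chi-squared |
|---|---|---|
| 4% | 62% | 65% |
| 5% | 72% | 77% |
| 6% | 80% | 85% |
| 8% | 90% | 94% |
| 10% | 96% | 98% |

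The exact column sums the two binomial distributions over all tables that the test rejects. Sections 3.6 and 5.2 do not say whether the chi-squared test is continuity-corrected. With the correction, exact power at 6% against 1% is 76%. The formula's 80% lies between the two exact values.

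**Sensitivity to the other input.** Keep the control risk at 6% and 211 per arm. A relative risk of 0.25 gives 68% by formula, and 0.33 gives 56% (both values assumed). An error in the assumed effect therefore matters on the same scale as an error in the control risk.

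**The literal monthly reading.** Suppose 0.06 and 0.01 were risks per patient over 30.4 days, with constant hazard and a common stay of t days (all assumptions). The risk over the stay is 1 − (1 − p)^(t/30.4).

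| Stay | Control | Intervention | Power, formula, 211 per arm |
|---|---|---|---|
| 7 days | 1.4% | 0.2% | 27% |
| 14 days | 2.8% | 0.5% | 48% |
| 21 days | 4.2% | 0.7% | 64% |
| 45 days | 8.8% | 1.5% | 93% |

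These rows cannot be taken as estimates. The documents give no expected stay, and section 7.3 (Consent) states that risk is highest in the first days after admission. That contradicts a constant hazard and means such scaling understates the risk of a short stay. The reading itself is also not established: a proportion reported each month and then averaged would carry the same label and would need no rescaling.

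**Loss allowance.** 422 × 1.10 = 464.2, the plan's 464. Dividing instead gives 422/0.90 = 468.9. A 10% loss from 464 leaves 417.6, about 209 per arm, with power 79.6% by formula against 80.0%. The loss actually covered is (464 − 422)/464 = 9.05%.

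All power figures ignore the interim futility stop in section 6.2, which can only lower them.

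**The case for a change.** The strongest case for a change is that the control risk is one of only two rates behind the sample size, that power responds steeply to it, and that the sponsor already holds the data to define it. A definition plus a power table would cost almost nothing. The caveat about higher incidence helps little: it concedes that 0.06 is not the trial population's heel and sacral rate, and it argues one direction only. Restriction to two sites, exclusion of category I (if the source counted it) and stays under a month all point the other way.

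Most of this is true as description. The input is undefined, and a reader cannot confirm 80% from the text. What does not follow is that the plan is wrong. The site and category gap is firmer than the time-base gap, but its direction and size are unknown, because high-risk selection and follow-up on general wards act against the downward factors. Nothing in the documents supplies a better control rate, so no different sample size can be derived from them. The request comes down to a sentence of definition, and if 0.06 already is the per-patient proportion of the right ulcers, even that sentence would alter nothing.

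**Conclusion.** No change to the plan is called for. This is a missing definition that a statistician reading section 3.6 fills in the natural way: the figure is paired with a cumulative incidence, a relative risk is formed from the two, and 211 per arm comes out exactly. The documents do not show that the trial is mis-sized in either direction.

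The gap does not reach the analysis. The primary test in section 5.2 compares observed proportions, and section 6.2 bases conditional power on observed data, so a wrong planning rate would affect the chance of a positive result but not the validity of the test or its type I error. Its possible effect on power is not small: 62% to 96% over control risks of 4% to 10%, by formula at 211 per arm with the relative risk fixed at 1/6 and no interim stop. That range describes ordinary uncertainty about a planning rate, which the section partly acknowledges, and no figure in the documents favours one end of it.

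The loss allowance is a clerical slip from a common shortcut. It provides for about 9% rather than 10%, costs about 0.4 percentage points of power at the stated loss, and changes no conclusion.

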## **4 Methods: assignment of interventions**

### **4.1 Assignment of interventions**

A simple randomisation with a 1:1 allocation as per computer generated randomisation table will be used. The randomisation table will be created at the Department of Biometry and Clinical Epidemiology independently from the CRC.

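### Minor slip in section 3.6: 464 is 422 plus 10%, which covers a loss of about 9%; a 10% loss needs 469 (470 with equal arms)

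*Combined protocol and SAP*

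**What the plan says.** Section 3.6 (Sample size) builds the enrolment target in two steps.

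- **Number needed.** The authors write "we will need to study 211 experimental patients and 211 control patients" to reject equality of the two incidences "with a probability (power) of 0.8", at a two-sided type I error of 0.05. The control figure is from internal data: "the average PU incidence at the ICUs of the Charité is 0.06 per month". The expected figure under the dressings is 0.01. The test is named: "We will use the chi-squared test statistic to evaluate this null hypothesis". The total of 422 is the sum of the two arms; the section does not print it.
- **Allowance for loss.** "To prevent a possible loss of follow-up of 10%, 464 patients in total are to be included". No inflation formula is given.

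Three other sections bear on the point. Section 4.1 specifies simple 1:1 randomisation, section 5.2 an intention-to-treat analysis, and section 6.2 one interim analysis at 50% of the sample, n = 232.

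**The concern.** The purpose of 464 is stated: it is there to absorb a 10% loss to follow-up, so the required number should still be available after that loss. Adding 10% to the required number does not achieve this, because the loss is then taken from the larger, enrolled number. The required number has to be divided by the retained fraction.

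What is at stake is the accuracy of the sample-size justification. Number needed, loss allowance, enrolment and power are presented as a matching set, and they do not quite match. At 211 per arm the calculated power is 80.02%, so there is almost no rounding margin and even a small shortfall takes it below the stated 0.8.

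**Working it through.** **Inputs.** Section 3.6: control 0.06, intervention 0.01, two-sided alpha 0.05, power 0.80, chi-squared test with no continuity correction mentioned, 10% loss, 464 enrolled. Section 4.1: 1:1 allocation. The monthly 0.06 is taken as a cumulative proportion, as the plan does; whether that is sound is a separate question.

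**1. Reproduce 211 per arm.** With mean proportion 0.035 and the pooled-variance formula

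n = [1.960 x sqrt(2 x 0.035 x 0.965) + 0.842 x sqrt(0.06 x 0.94 + 0.01 x 0.99)]^2 / 0.05^2

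the square roots are 0.2599 and 0.2575, and n = 210.9, so 211. The plan's figure reproduces exactly. Power at 211 per arm is 80.02%. (With continuity correction n would be 250, and with unpooled variance 208.2, so 209; neither gives 211.)

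**2. Reproduce 464.**
- 2 x 211 = 422
- 422 x 1.10 = 464.2, which gives the stated 464
- 422 / 0.90 = 468.9, which does not

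The allowance was therefore made by adding 10%.

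**3. Apply a 10% loss to 464.**
- 464 x 0.90 = 417.6, about 418, or 208.8 per arm
- 422 - 417.6 = 4.4, so 4 to 5 patients short
- Largest loss that leaves 422: 464 - 422 = 42, and 42/464 = 9.05%

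**4. Number that does cover 10%.**
- 422 / 0.90 = 468.9, so 469 in total
- With equal arms: 211 / 0.90 = 234.4, so 235 per arm and 470 in total; 235 x 0.90 = 211.5, which meets 211

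**5. Effect on fixed-sample power.** By the formula in step 1, solved for power:

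power = Phi{[0.05 x sqrt(n) - 1.960 x 0.2599] / 0.2575}

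| Analysed per arm | Power |
|---|---|
| 208.8 (464 enrolled, 10% lost) | 79.6% |
| 211 (number required) | 80.0% |
| 232 (464 enrolled, all analysed) | 83.6% |

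The cost of the slip is 80.02 - 79.60, about 0.4 percentage points.

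**6. Interim size.** 464 / 2 = 232, which agrees with section 6.2.

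**The case against.** **The effect is trivial.** This stands. The shortfall of about 2 per arm is smaller than the uncertainty in the inputs. Under the unpooled-variance formula, 208.8 per arm still gives 80.1%, although that formula does not reproduce 211. A control incidence of 0.0605 instead of 0.06 also restores 80.1%, and section 3.6 itself expects that the true incidence may be higher. Under simple randomisation of 464 patients the standard deviation of one arm's size is sqrt(464 x 0.25) = 10.8, about five times the shortfall per arm. For the same reason 208.8 and 235 per arm are only nominal figures.

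**Under intention to treat nobody is lost.** This stands in part. Section 5.2 does not say how patients lost to follow-up count in the primary test. Section 3.3 makes discharge, transfer, death, withdrawal and severe protocol violation ends of follow-up, so such patients have an outcome status up to that time. If all 464 are analysed there is no shortfall. However, an allowance for loss has a purpose only if lost patients reduce the usable number, so the plan is being held to its own premise. Section 7.3 also deletes the data of patients who were included before consent when participation is then declined. The documents do not say that this group is the 10%.

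**Adding 10% is a common rough allowance.** True, and the plan does not state in words that 422 remain after a 10% loss. It does offer 464 as the protection against that loss, and measured against that purpose 464 covers 9%.

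**Stronger readings that the documents do not support.**
- A reader might infer that the trial is underpowered. A gap of 0.4 points does not show that.
- A reader might infer that the interim size is wrong. It is exactly half of the stated total.
- A reader might take 79.6% as the trial's power. It is a fixed-sample figure that ignores the futility rule in section 6.2 (stop if conditional power is below 60% at the halfway point). That rule can only lower the overall power.

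**Conclusion.** The point holds as a minor arithmetic slip. The enrolment of 464 was obtained by multiplying 422 by 1.10, whereas covering a 10% loss needs 469, or 470 with equal arms. At 10% loss about 418 remain, 4 to 5 fewer than required, and fixed-sample power is about 79.6% instead of 80.0%.

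This rests on three assumptions: lost patients are not analysed, the arms are equal in size, and power is computed with the pooled-variance formula that reproduces the plan's 211. If the first fails and all 464 are analysed, the shortfall disappears. No analysis or conduct decision depends on the difference. Severity is the lowest: a statement to correct, with no consequence for the design.

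**What to change.** Replace the loss-to-follow-up sentence in section 3.6 with, for example:

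> With 464 patients included, the required 422 remain evaluable if loss to follow-up is at most 9%; at 10% loss about 418 remain.

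If a power figure is added, label it as fixed-sample power before the futility rule in section 6.2 is applied, and state that it assumes lost patients are not analysed.

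The cost is one sentence and a slightly less favourable stated allowance. Enrolment stays at 464 and the interim size at 232. Only if the sponsor prefers to keep 10% as the stated allowance do the totals change: 470 enrolled with equal arms, and half of that, 235, at the interim analysis. A gap of this size does not call for that.
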